7.3.2. Safety Subgroup Analysis

A summary of the number and percentage of subjects who experience a solicited and unsolicited AE during Days 1 through 29 by SOC and PT will be presented by race group – white or non-white – and gender.

7.4. Prior and Concomitant Medications

Only medications taken from 30 days prior to vaccination through study termination will be recorded.

Any medications started and stopped prior to or on the date of vaccination will be considered prior medications. If a partial stop date is entered and the month and year (if day is missing) or year (if day and month are missing) of the stop date are before the date of vaccination, the medication will be considered a prior medication.

Any medications started prior to or on the date of vaccination and continued to be taken after vaccination, or started after the date of vaccination, will be considered a concomitant medication. If a partial stop date is entered and the month and year (if day is missing) or year (if day and month are missing) of the stop date are after the date of vaccination, the medication will be considered a concomitant medication.

Concomitant medications (i.e., medications other than study vaccine that are taken while receiving study vaccine) and prior medications (medications started and ended before receiving study vaccine) will be coded using the World Health Organization (WHO) Drug Dictionary version September 2017. The WHO preferred name and drug code will be attached to the clinical database. All concomitant medications associated with unsolicited AEs will be documented through Day 29. Concomitant medications associated with SAEs will be documented through Day 182.

Use of concomitant and prior medications up to and including Day 29 will be summarized (number and percentage of subjects) by study arm, WHO drug class (ATC level 4), and WHO generic name. Multiple drug use (by preferred name) will be counted once only per subject. The summary will be sorted alphabetically by drug class and then by decreasing total frequency within a class. Concomitant medications reported with start dates after Day 29 through Day 182 for all subjects will be listed.

Summaries of prior and concomitant medications will be provided for the safety population. No p-values or inferences regarding comparisons of the usage of concomitant medications in the two study arms will be generated.

A listing of prior and concomitant medications will be provided, with a column indicating if a medication is prior, Y or N. Any exposed subjects who received an excluded concomitant medication will be provided in a separate listing.

7.5. Vital Signs

Vital signs will be listed by subject and time point for the exposed population.

7.6. Physical Examination

A data listing will be provided for physical examination results based on the exposed population.

7.7. Other Safety Measures

A data listing of all pregnancy test results as well as a data listing of HBV, HCV and HIV test results will be provided for exposed subjects.

8. CHANGES TO STATISTICAL METHODS IN THE PROTOCOL

The population labeled “Study Population” in the protocol has been renamed the “Enrolled Population.”

In response to an issue raised by the FDA following a review of the study protocol, the following requirement was added to the definition of the immunogenicity evaluable population:

In addition, all subjects in the alphavirus-naïve group are required to be seronegative for both neutralizing CHIKV and VEEV antibodies at baseline.

A titer of [REDACTED] was added to the summaries of the secondary immunogenicity endpoints identified as the proportion of subjects with titers of at least [REDACTED]. This addition was made to provide better profiling of the distribution of titers and to match data from other studies.

Fisher’s exact tests were specified in the protocol as the primary method for comparing alphavirus-naïve subjects to alphavirus-prior subjects. Logistic regression models that incorporated age and gender were also specified as sensitivity analyses for these endpoints. However, the models proved problematic, and in some cases impossible, to fit because of the high seroconversion rate in both groups. Thus, the logistic regression analyses were eliminated.

10. SOFTWARE

SAS Software Version 9.4. SAS Institute Inc., Cary, NC, USA.

11. LIST OF TABLES, FIGURES, AND LISTINGS

Tables

Table	Title
14.1.1	Summary of Subjects by Site - Exposed Population
14.1.2	Analysis Populations - All Subjects
14.1.3	Subject Disposition - Exposed Population
14.1.4.1	Demography - Safety Population
14.1.4.2	Demography - mITT Population
14.1.4.3	Demography - Immunogenicity Evaluable Population
14.1.5	Medical History - Safety Population
14.1.6	Timing of Blood Sample Collection - Safety Population
14.1.7.1	Important Protocol Deviations - Exposed Population
14.1.7.2	Reasons for Exclusion from Analysis Populations - Exposed Population
14.2.1.1.1	Primary Endpoint: Neutralizing Antibody Seroresponse Against Chikungunya at Day 22 - Immunogenicity Evaluable Population
14.2.1.1.2	Primary Endpoint: Neutralizing Antibody Seroresponse Against Chikungunya at Day 22 - mITT Population
14.2.1.3.1	Neutralizing Antibody Seroresponse Against Chikungunya - Immunogenicity Evaluable Population
14.2.1.3.1.1	Neutralizing Antibody Seroresponse Against Chikungunya by Race - Immunogenicity Evaluable Population
14.2.1.3.1.2	Neutralizing Antibody Seroresponse Against Chikungunya by Gender - Immunogenicity Evaluable Population
14.2.1.3.2	Neutralizing Antibody Seroresponse Against Chikungunya - mITT Population
14.2.1.4.1	Geometric Mean Neutralizing Antibody Titer Against Chikungunya - Immunogenicity Evaluable Population
14.2.1.4.1.1	Geometric Mean Neutralizing Antibody Titer Against Chikungunya by Race - Immunogenicity Evaluable Population
14.2.1.4.1.2	Geometric Mean Neutralizing Antibody Titer Against Chikungunya by Gender - Immunogenicity Evaluable Population
14.2.1.4.2	Geometric Mean Neutralizing Antibody Titer Against Chikungunya - mITT Population
14.2.1.5.1	Geometric Mean Fold Increase in Neutralizing Antibody Titer Against Chikungunya - Immunogenicity Evaluable Population
14.2.1.5.2	Geometric Mean Fold Increase in Neutralizing Antibody Titer Against Chikungunya - mITT Population
14.2.1.6.1	Percentage of Subjects with Anti-Chikungunya Neutralizing Activity At or Above Selected Thresholds by Time Point - Immunogenicity Evaluable

Table	Title
	Population
14.2.1.6.1.1	Percentage of Subjects with Anti-Chikungunya Neutralizing Activity At or Above Selected Thresholds by Time Point and Race - Immunogenicity Evaluable Population
14.2.1.6.1.2	Percentage of Subjects with Anti-Chikungunya Neutralizing Activity At or Above Selected Thresholds by Time Point and Gender - Immunogenicity Evaluable Population
14.2.1.6.2	Percentage of Subjects with Anti-Chikungunya Neutralizing Activity At or Above Selected Thresholds by Time Point - mITT Population
14.2.1.7.1	Cumulative Percentage of Subjects with Anti-Chikungunya Neutralizing Activity Above Selected Thresholds by Time Point - Immunogenicity Evaluable Population
14.2.1.7.2	Cumulative Percentage of Subjects with Anti-Chikungunya Neutralizing Activity Above Selected Thresholds by Time Point - mITT Population
14.2.2.1	Total Antibody Seroresponse Against Chikungunya - Immunogenicity Evaluable Population
14.2.2.2	Geometric Mean Total Antibody Titer Against Chikungunya - Immunogenicity Evaluable Population
14.2.2.3	Geometric Mean Fold Increase in Total Antibody Titer Against Chikungunya - Immunogenicity Evaluable Population
14.2.2.4	Percentage of Subjects with Anti-Chikungunya Total Antibody Activity At or Above Selected Thresholds by Time Point - Immunogenicity Evaluable Population
14.2.3.1	Neutralizing Antibody Seroresponse Against VEEV - Immunogenicity Evaluable Population
14.2.3.2	Geometric Mean Neutralizing Antibody Titer Against VEEV - Immunogenicity Evaluable Population
14.2.3.3	Geometric Mean Fold Increase in Neutralizing Antibody Titer Against VEEV - Immunogenicity Evaluable Population
14.2.3.4	Percentage of Subjects with Anti-VEEV Neutralizing Activity At or Above Selected Thresholds by Time Point - Immunogenicity Evaluable Population
14.2.4.1	Total Antibody Seroresponse Against VEEV - Immunogenicity Evaluable Population
14.2.4.2	Geometric Mean Total Antibody Titer Against VEEV - Immunogenicity Evaluable Population
14.2.4.3	Geometric Mean Fold Increase in Total Antibody Titer Against VEEV - Immunogenicity Evaluable Population
14.2.4.4	Percentage of Subjects with Anti-VEEV Total Antibody Activity At or Above Selected Thresholds by Time Point - Immunogenicity Evaluable Population
14.2.5.1	Percentage of Subjects with a Fold Increase in Chikungunya-specific IFN-g at or Above Selected Thresholds by Time Point - Immunogenicity Evaluable Population

Table	Title
14.2.5.2	Chikungunya-specific IFN-g ELISPOT Response - Immunogenicity Evaluable Population
14.2.5.3	Percentage of Subjects with a Fold Increase in VEEV-specific IFN-g at or Above Selected Thresholds by Time Point - Immunogenicity Evaluable Population
14.2.5.4	VEEV-specific IFN-g ELISPOT Response - Immunogenicity Evaluable Population
14.3.1	High Level Summary of All Solicited and Unsolicited Events - Safety Population
14.3.1.1	Solicited Events by Highest Reported Severity- Safety Population
14.3.1.2	Solicited Events of at Least Severe (Grade 3) Severity- Safety Population
14.3.1.3	Treatment-related Solicited Events by Highest Reported Severity- Safety Population
14.3.2.1	Day of Onset for Subjects who Reported Solicited Events- Safety Population
14.3.2.2	Day of Onset for Subjects who Reported Treatment-related Solicited Events - Safety Population
14.3.3.1	Number of Days with Symptoms for Subjects who Reported Solicited Events- Safety Population
14.3.3.2	Number of Days with Symptoms for Subjects who Reported Treatment-Related Solicited Events - Safety Population
14.3.4	Percentage of Subjects with Solicited Events by Day on Study- Safety Population
14.4.1	Listing of Serious Adverse Events Leading to Death - Safety Population
14.4.2	Listing of Serious Adverse Events - Safety Population
14.4.3.1	Serious Adverse Events by System Organ Class and Preferred Term - Safety Population
14.4.3.2	Treatment-related Serious Adverse Events by System Organ Class and Preferred Term - Safety Population
14.4.4.1	Unsolicited Adverse Events by Preferred Term in Descending Order of Incidence Through Day 29 - Safety Population
14.4.4.2	Unsolicited Adverse Events of Severe or Higher Severity by Preferred Term in Descending Order of Incidence Through Day 29 - Safety Population
14.4.5.1	Unsolicited Adverse Events Through Day 29 by System Organ Class and Preferred Term - Safety Population
14.4.5.2	Solicited and Unsolicited Adverse Events Through Day 29 by System Organ Class and Preferred Term - Safety Population
14.4.5.2.1	Solicited and Unsolicited Adverse Events Through Day 29 by System Organ Class and Preferred Term by Race - Safety Population
14.4.5.2.2	Solicited and Unsolicited Adverse Events Through Day 29 by System Organ Class and Preferred Term by Gender - Safety Population
14.4.6	Unsolicited Adverse Events Through Day 29 by System Organ Class, Preferred Term, and Highest Reported Severity - Safety Population

Table	Title
14.4.7	Unsolicited Adverse Events Leading to Withdrawal by System Organ Class and Preferred Term - Safety Population
14.4.8	Treatment-related Unsolicited Adverse Events by Preferred Term in Descending Order of Incidence Through Day 29 - Safety Population
14.4.9.1	Treatment-related Unsolicited Adverse Events Through Day 29 by System Organ Class and Preferred Term - Safety Population
14.4.9.2	Treatment-related Solicited and Unsolicited Adverse Events Through Day 29 by System Organ Class and Preferred Term - Safety Population
14.4.10	Treatment-related Unsolicited Adverse Events Through Day 29 by System Organ Class, Preferred Term, and Highest Reported Severity - Safety Population
14.4.11	Treatment-related Unsolicited Adverse Events Leading to Withdrawal by System Organ Class and Preferred Term - Safety Population
14.5.1	Prior and Concomitant Medications by Descending Frequency within ATC Class Through Day 29 - Safety Population

Figures

Figure	Title
14.2.2.1	Reverse Cumulative Distribution of Neutralizing Antibody Titer Against Chikungunya at Day 22 - Immunogenicity Evaluable Population
14.2.2.2	Reverse Cumulative Distribution of Fold Increase in Neutralizing Antibody Titer Against Chikungunya at Day 22 - Immunogenicity Evaluable Population
14.2.2.3	Geometric Mean Neutralizing Antibody Titer Against Chikungunya Over Time - Immunogenicity Evaluable Population
14.2.2.4	Geometric Mean Fold Increase in Neutralizing Antibody Titer Against Chikungunya Over Time - Immunogenicity Evaluable Population
14.2.2.5	Reverse Cumulative Distribution of Neutralizing Antibody Titer Against VEEV at Day 22 - Immunogenicity Evaluable Population
14.2.2.6	Reverse Cumulative Distribution of Fold Increase in Neutralizing Antibody Titer Against VEEV at Day 22 - Immunogenicity Evaluable Population
14.2.2.7	Geometric Mean Neutralizing Antibody Titer Against VEEV Over Time - Immunogenicity Evaluable Population
14.2.2.8	Geometric Mean Fold Increase in Neutralizing Antibody Titer Against VEEV Over Time - Immunogenicity Evaluable Population

Listings

Listing	Title
16.2.1.1	Subject Disposition - Exposed Population
16.2.1.2	Reasons for Screen Failure
16.2.2.1	Subjects Who Received an Excluded Concomitant Medication - Exposed Population
16.2.2.2	Important Protocol Deviations - Exposed Population
16.2.3.1	Analysis Populations - All Subjects
16.2.4.1	Demography - Enrolled Population
16.2.4.2	Medical History - Exposed Population
16.2.4.3	Verbatim to Summary Term Mapping for Medical History - Exposed Population
16.2.5.1	Study Vaccine Administration Data - Exposed Population
16.2.6.1	Anti-Chikungunya Neutralizing Antibody and Total Antibody Titers - Exposed Population
16.2.6.2	Anti-VEEV Neutralizing Antibody and Total Antibody Titers - Exposed Population
16.2.6.3	IFN- γ ELISPOT Response - Exposed Population
16.2.7.1	Solicited Events - Safety Population

1. BACKGROUND AND RATIONALE

This addendum is to officially document the removal of certain tabular summaries from the final Clinical Study Report Tables.

2. STATISTICAL CONSIDERATIONS

The Statistical Analysis Plan (SAP) called for the following secondary endpoints:

Anti-CHIKV total antibodies, determined by immunoassay, in prior alpha subjects vs. naïve alpha subjects, assessed by

- The proportion of subjects with titers of at least [REDACTED] on Days 1, 22 and 29

Anti-VEEV total antibodies, determined by immunoassay, in prior alpha subjects vs. naïve alpha subjects, assessed by

- The proportion of subjects with titers of at least [REDACTED] at Days 1, 22 and 29

It was determined post database lock, that the threshold analysis of the anti-CHIKV total and anti-VEEV total antibodies had no valuable meaning with respect to historical sero-epidemiologic protection. Therefore, the CSR team decided that these summaries should be eliminated from the final set of tables.

Also included in the original TOC for the mock tables were cumulative percentages of subjects reaching 4-fold. Because all subjects experienced 4-fold rise by the second timepoint and the groups remained at 100% throughout the study, these tables (mITT and IEP) were considered moot and not produced (they exactly mimic the by-visit summary table).

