2.4.3 Secondary Immunogenicity Endpoints

- Anti-CHIKV neutralizing antibodies, determined by luciferase-based assay (NT₈₀), in prior alphavirus vaccine recipients versus alphavirus-naïve controls, assessed by
 - Geometric mean titer (GMT) and geometric mean ratio (GMR) on Days 1, 8, 22, 29, 57 and 182.
 - Seroconversion rates on Days 8, 29, 57 and 182.
 - The proportion of subjects with titers of at least 40, 160 or 640 on Days 1, 8, 22, 29, 57 and 182.
- Anti-CHIKV total antibodies, determined by immunoassay, in prior alphavirus vaccine recipients versus alphavirus-naïve controls, assessed by
 - GMT and GMR on Days 1, 22 and 29.
 - Seroconversion rate on Days 22 and 29, where seroconversion is a 4-fold rise in titer over baseline.
 - The proportion of subjects with titers of at least 40, 160 or 640 on Days 1, 22 and 29.
- Anti-VEEV total and neutralizing antibody, as determined by an immunoassay and a Plaque-Reduction Neutralization Test (PRNT₈₀) respectively, in prior alphavirus vaccine recipients versus alphavirus-naïve controls, assessed by
 - GMT and GMR on Days 1, 22 and 29.
 - Seroconversion rate on Days 22 and 29, where seroconversion is a 4-fold rise in titer over baseline.
 - The proportion of subjects with titers of at least 40, 160 or 640 on Days 1, 22 and 29.

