9.6 Immunogenicity Analysis

All tests will be carried out at a 2-sided significance level of 0.05 and no adjustment for multiplicity will be applied.

Seroconversion Analysis:

The primary immunogenicity analysis will compare prior alphavirus vaccine recipients to alphavirus-naïve controls on the proportion in each group who seroconvert by anti-CHIKV neutralizing antibody at Day 22. Seroconversion is defined as a 4-fold or greater rise over baseline in anti-CHIKV neutralizing antibodies as assessed by a luciferase-based assay.

Specifically, we will test the hypotheses:

$$H_0: P_1 = P_2 \text{ vs. } H_1: P_1 \neq P_2$$

where P_1 and P_2 denote the proportion of subjects who seroconvert in the prior alphavirus vaccine recipients and the alphavirus-naïve controls, respectively.

The significance of the comparison of the pre-exposure groups will be assessed using a Fisher's exact test. The percentage who seroconvert in each group will be presented along with its 95% CI calculated using the Wilson method. A sensitivity analysis of the comparison will be performed using a logistic regression model that incorporates age, gender, and baseline titer as potential predictive factors. Fisher's test comparing seroconversion rates at other time points may also be performed. Similar analyses of the proportion who seroconvert will be conducted on Days 8, 29, 57 and 182 for anti-CHIKV neutralizing antibody and on Days 22 and 29 for total anti-CHIKV, total anti-VEEV and neutralizing anti-VEEV antibodies (secondary endpoints).

Threshold analyses:

The percentage of subjects achieving specified thresholds (e.g., ≥ 40 , 160, and 640 anti-CHIKV antibody titers), and associated Wilson 95% CIs, will also be calculated for Days 1, 8, 22, 29, 57 and 182 for neutralizing antibody and at Days 1, 22 and 29 for total anti-CHIKV, total anti-VEEV and neutralizing anti-VEEV antibodies (secondary end-points). The groups will be compared by pairwise Fisher's exact tests on the percentage achieving each threshold.

GMT analyses:

For the secondary comparisons based on GMT, the hypotheses tested will be

$$H_0: \mu_1 = \mu_2 \text{ vs. } H_1: \mu_1 \neq \mu_2$$

where μ_1 and μ_2 denote the GMT for the prior alphavirus vaccine recipients and the alphavirus-naïve controls, respectively.

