6.2. Secondary Immunogenicity Endpoints

Secondary immunogenicity endpoints include:

- Anti-CHIKV neutralizing antibodies, determined by luciferase-based assay (NT80), in prior alpha subjects vs. naïve alpha subjects, assessed by
 - Seroconversion rates on Days 8, 29, 57 and 182
 - GMT and GMR on Days 1, 8, 22, 29, 57 and 182
 - The proportion of subjects with titers of at least 40, 100, 160 or 640 on Days 1, 8, 22, 29, 57 and 182
- Anti-CHIKV total antibodies, determined by immunoassay, in prior alpha subjects vs. naïve alpha subjects, assessed by
 - Seroconversion rates on Days 22 and 29 where seroconversion is a 4-fold rise in titer over baseline
 - GMT and GMR on Days 1, 22 and 29

- The proportion of subjects with titers of at least 40, 100, 160 or 640 on Days 1, 22 and 29
- Anti-VEEV neutralizing antibodies, determined by Plaque-Reduction Neutralization Test (PRNT80) assay, in prior alpha subjects vs. naïve alpha subjects, assessed by
 - Seroconversion rate on Days 22 and 29 where seroconversion is a 4-fold rise in titer over baseline
 - GMT and GMR on Days 1, 22 and 29
 - The proportion of subjects with titers of at least 40, 100, 160 or 640 at Days 1, 22 and 29
- Anti-VEEV total antibodies, determined by immunoassay, in prior alpha subjects vs. naïve alpha subjects, assessed by
 - Seroconversion rate on Days 22 and 29 where seroconversion is a 4-fold rise in titer over baseline
 - GMT and GMR on Days 1, 22 and 29
 - The proportion of subjects with titers of at least 40, 100, 160 or 640 at Days 1, 22 and 29

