An additional analysis of geometric mean of the fold-increase in titer over baseline will be provided. The geometric mean and median fold-increase in titer over baseline will be presented at each visit. To calculate the geometric mean fold-increase and 95% CI, the fold-increase results will be \log_{10} -transformed, the mean and 95% CI of these transformed data will be calculated and then exponentiated to convert to the non-transformed scale. A t-test will be used to compare the \log_{10} -transformed fold increase between the prior alpha and naive alpha subjects. The median, minimum and maximum of the fold-increase in titer over baseline will be summarized based on the non-transformed scale.

The percentage of subjects achieving specified thresholds (40, 100, 160, and 640 anti-CHIKV neutralizing antibody titers), and associated Wilson 95% CIs, will be summarized at Days 1, 8, 22, 29, 57 and 182 for anti-CHIKV neutralizing antibodies and at Days 1, 22 and 29 for anti-CHIKV total, anti-VEEV total, and anti-VEEV neutralizing antibodies. The groups will be compared by pairwise Fisher's exact tests on the percentage achieving each threshold. An additional summary will be provided for the cumulative percentage of subjects reaching the specified thresholds of anti-CHIKV neutralizing antibody titers.

All secondary analyses will be performed for the IEP. The secondary analysis of anti-CHIKV neutralizing antibodies as determined by luciferase-based assay will be repeated on the mITT population.

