3. LIST OF FINAL REPORT TABLES, LISTINGS AND FIGURES

The following tables specified in the SAP mock table TOC, corresponding to the removed deleted analyses, have been removed.

- 14.2.1.7.1 Cumulative Percentage of Subjects with Anti-Chikungunya Neutralizing Activity At or Above Selected Thresholds by Time Point; Immunogenicity Evaluable Population
- 14.2.1.7.2 Cumulative Percentage of Subjects with Anti-Chikungunya Neutralizing Activity At or Above Selected Thresholds by Time Point; mITT Population
- 14.2.2.4 Percentage of Subjects with Anti-Chikungunya Total Antibody Activity At or Above Selected Thresholds by Time Point; Immunogenicity Evaluable Population
- 14.2.4.4 Percentage of Subjects with Anti-VEEV Total Antibody Activity At or Above Selected Thresholds by Time Point; Immunogenicity Evaluable Population

STATISTICAL ANALYSIS PLAN

ADDENDUM Number # 2

Protocol EBSI-CV-317-002

A Phase 2 Open-Label Study to Assess the Safety and Immunogenicity of an Alum-Adjuvanted Chikungunya Virus-Like Particle Vaccine (PXVX0317) in Prior Recipients of Other Alphavirus Vaccines Versus Alphavirus Naïve Controls

23 Feb 2024

CONFIDENTIAL AND PROPRIETARY INFORMATION

Signature Page

Biostatistician	Dated electronically (Date)	See electronic signature
Author		
Medical Writer	Dated electronically (Date)	See electronic signature
Medical Monitor	Dated electronically (Date)	See electronic signature
Biostatistician Reviewer	Dated electronically (Date)	See electronic signature

[Redacted signatures]

TABLE OF CONTENTS

SIGNATURE PAGE.....	2
TABLE OF CONTENTS.....	3
LIST OF ABBREVIATIONS.....	4
1. BACKGROUND AND RATIONALE	5
2. STATISTICAL CONSIDERATIONS	5
3. LIST OF FINAL REPORT TABLES, LISTINGS AND FIGURES	8

LIST OF ABBREVIATIONS

ADaM	Analysis Data Model
CDISC	Clinical Data Interchange Standards Consortium
CSR	Clinical Study Report
IEP	Immunogenicity Evaluable Population
PRNT	Plaque-reduction Neutralizing Titer
SAP	Statistical Analysis Plan
SDTM	Study Data Tabulation Model
TOC	Table of Contents

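### After database lock, SAP Addendum 1 drops the threshold proportions for total anti-CHIKV and total anti-VEEV antibody, and it deletes two cumulative titer tables for a reason that belongs to a different measure

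*SAP*

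**What the plan says.** **Total antibody.** Protocol 2.4.3 lists this among the secondary endpoints, for total anti-CHIKV antibody and again for anti-VEEV antibody: "The proportion of subjects with titers of at least 40, 160 or 640 on Days 1, 22 and 29". Protocol 9.6 repeats the secondary label and calls for a Fisher's exact test between groups at each threshold. SAP 6.2 keeps the endpoint and adds a cut-off of 100: "The proportion of subjects with titers of at least 40, 100, 160 or 640 on Days 1, 22 and 29". The corresponding tables in SAP section 11 are 14.2.2.4 and 14.2.4.4.

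Addendum 1, section 2, itself describes these items as secondary endpoints and then states: "It was determined post database lock, that the threshold analysis of the anti-CHIKV total and anti-VEEV total antibodies had no valuable meaning". It goes on to explain that the meaning at issue is protection, and it removes both tables. (The addendum's number is inferred from its place before Addendum 2. Its cut-offs are redacted and are read here from the protocol and SAP.)

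**Cumulative neutralizing tables.** SAP 6.2.1 promises: "An additional summary will be provided for the cumulative percentage of subjects reaching the specified thresholds of anti-CHIKV neutralizing antibody titers". It gives the thresholds as 40, 100, 160 and 640. The SAP table list titles 14.2.1.7.1 "Cumulative Percentage of Subjects with Anti-Chikungunya Neutralizing Activity Above Selected Thresholds by Time Point - Immunogenicity Evaluable Population", with a matching table for the mITT population. Addendum 1, section 2, describes the tables instead as cumulative percentages with a 4-fold rise and calls them moot: "Because all subjects experienced 4-fold rise by the second timepoint and the groups remained at 100% throughout the study". It adds that they would duplicate the by-visit table. Yet its own section 3 names the first deleted table as "14.2.1.7.1 Cumulative Percentage of Subjects with Anti-Chikungunya Neutralizing Activity At or Above Selected Thresholds by Time Point; Immunogenicity Evaluable Population".

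**The concern.** Two things look wrong.

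First, part of two listed secondary endpoints was withdrawn once the database was locked, in an open-label study, for a reason that was available beforehand. The same section of the addendum cites study results, so its authors knew some outcomes when they wrote it. Nothing suggests that an unfavourable result was hidden, but the timing lets a reader ask, and the question was avoidable.

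Second, the reason for deleting the cumulative tables concerns fold rise, while the tables concern absolute titers. If the reason does not cover them, an analysis that the SAP promised was dropped without a valid explanation on record.

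**Working it through.** The plan gives no figure of its own on this point. Its power calculation is not involved: the exact Fisher power for 95% versus 65% with 30 per group recomputes to 78.8% against the stated 80%, and nothing here changes it.

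**1. Size of the total-antibody removal**

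Inputs: 2 assays; 3 days (1, 22, 29); 3 cut-offs in the protocol (40, 160, 640) or 4 in the SAP (40, 100, 160, 640).

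| | Protocol cut-offs | SAP cut-offs |
|---|---|---|
| All comparisons | 2 × 3 × 3 = 18 | 2 × 3 × 4 = 24 |
| Day 1 only | 2 × 1 × 3 = 6 | 2 × 1 × 4 = 8 |
| Post-vaccination | 18 − 6 = 12 | 24 − 8 = 16 |

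The new and revised table lists in Addendum 2, section 3, do not bring either table back.

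**2. Does a universal 4-fold rise settle the cumulative threshold tables?**

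Inputs: the limit of detection for the CHIKV neutralization assay is 15 (SAP 3.1.5), and values below it are set to 15 when fold rise is calculated (SAP 3.3). The lowest titer that counts as a 4-fold rise is therefore 4 × 15 = 60.

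| Cut-off | Fold rise needed from 15 | Assured by a 4-fold rise? |
|---|---|---|
| 40 | 40/15 = 2.7 | Yes (60 ≥ 40) |
| 100 | 100/15 = 6.7 | No |
| 160 | 160/15 = 10.7 | No |
| 640 | 640/15 = 42.7 | No |

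The stated reason is assured for 1 of 4 cut-offs.

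**3. Would the cumulative and by-visit tables have to agree?**

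No. A cumulative percentage cannot fall from visit to visit, but a by-visit percentage can as titers wane. Protocol 1.3.1 reports 100% seroconversion by Day 57 for every regimen in the earlier Phase 2 study, yet 44% above 1:640 at Day 182 for the regimen used here. Protocol 2.4.2 puts the peak for other single-dose regimens at Day 22.

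As an illustration, assume 44% as the Day 182 by-visit share at 640 in this trial. The cumulative share could then lie anywhere from 44% to 100%, a gap of 0 to 56 points. With 30 per arm, 0.44 × 30 = 13.2, about 13 subjects, so the gap is 0 to 30 − 13 = 17 subjects. This is only a logical bound. The 44% comes from another study and counts titers above, rather than at least, 640.

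**The case against.** The strongest reply on total antibody is that the removal was open and scientifically defensible. The addendum records what was removed, when, why and by whom. SAP 6.2.1 introduces the cut-offs as neutralizing titers and then applies them to immunoassays, and the documents offer no basis for them on that scale. Seroresponse, GMT and fold-rise tables for total antibody remain (14.2.2.1 to 14.2.2.3 and 14.2.4.1 to 14.2.4.3), as do Listings 16.2.6.1 and 16.2.6.2. No multiplicity adjustment was planned, so dropping tests alters no other test, and a third of the dropped comparisons are at Day 1. All of this stands and limits the harm. It does not explain why the decision waited until after lock. Lack of protective meaning also does not remove the descriptive use: SAP section 8 justifies an added cut-off as a way to show the spread of titers, and none of the eight planned figures covers total antibody.

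On the cumulative tables, the mock-table contents list that Addendum 1 cites is not available. It may have held 4-fold tables, in which case the titles rather than the reason would be wrong. That is possible. But SAP 6.2.1 would still have promised a cumulative titer summary that was dropped without a fitting explanation, and sections 2 and 3 of the addendum would still disagree. The cumulative tables are an SAP addition, not a protocol endpoint, and the by-visit threshold tables (14.2.1.6.1 and 14.2.1.6.2) remain.

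**Conclusion.** Both parts hold, as a minor point. The threshold component of two protocol-listed secondary endpoints was removed after lock for a reason that did not depend on the data: 18 comparisons by the protocol's cut-offs, 24 by the SAP's. The reason given for deleting the cumulative neutralizing tables is assured at 40 but not at 100, 160 or 640, and the claim that they must repeat the by-visit table does not follow.

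The floor of 60 rests on the SAP's detection limit and imputation rule. Whether cumulative and by-visit percentages actually differed in this trial cannot be told from the documents. No primary result is affected, and there is no sign that the removals concealed anything.

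**What to change.** - **Total antibody:** produce Tables 14.2.2.4 and 14.2.4.4 as planned, with a footnote such as: *Total-antibody thresholds have no established protective meaning; shown because this was a pre-specified secondary endpoint.*
- **Cumulative tables:** correct Addendum 1 so that its sections 2 and 3 agree with each other and account for the summary promised in SAP 6.2.1 and listed in section 11. Either restore 14.2.1.7.1 and 14.2.1.7.2 for 40, 100, 160 and 640, or give a reason that fits titer-threshold tables and report the omission in the study report as a post-lock change. If the mock tables did show 4-fold rise, correct the titles and still account for the missing titer summary.

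The cost is two short tables from existing data and specifications (four if the cumulative pair is restored) and a one-page correction. Addendum 2 already adds and reruns tables, so these could join a similar batch. The downside is a few extra tables of limited clinical meaning.
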